## 8.4. Guidelines and Evaluation

To promote consistency between assessments, the following guidelines should be taken into consideration along with good clinical judgment when documenting and recording AEs.

#### 8.4.1. Assessment and Recording

An AE, whether or not considered to be causally related to the treatment, must be promptly documented and recorded. At each study visit, after the subject has had an opportunity to spontaneously mention any problems, the investigator should inquire about AEs by asking the appropriate open questions. In addition to straightforward subject observation (e.g., headache, nausea, etc.), AEs will also be documented from any data collected in the CRF (e.g., laboratory values, physical examination findings, ECG changes, etc.) or other documents that are relevant to the safety of the subject.

At each follow-up visit or assessment by phone or otherwise, all AEs, whether observed by the investigator or other professional collaborators, or reported by the subject spontaneously or in response to an open question, will be recorded on the Adverse Event Form included in the CRF with the following information.

- Name of the AE: Name should be a medical term. When possible, the investigator should differentiate an illness entity from isolated symptoms or signs. For instance, the term “flu” should be recorded instead of listing all the flu-related symptoms. Where a differentiation is not possible, symptoms and signs should be separately recorded and evaluated as adverse events.
- Date of onset of the AE.
- Intensity: Event intensity will be assessed according to the CTCAE. If not described in the CTCAE, the intensity should be assessed according to the following categories: *Mild* (noticeable to the subject, does not interfere with the subject’s daily activities, usually does not require additional therapy, dose reduction, or discontinuation of the study); *Moderate* (interferes with the subject’s daily activities, possibly requires additional therapy, but does not require discontinuation of the study); *Severe* (severely limits the subject’s daily activities and may require discontinuation of the study); *Life-threatening*; *Death*.
- Date of resolution (or statement that the event is continuing).
- Action taken (e.g., concomitant medication or adjunctive therapy given will be recorded on the Concomitant Medications Form or the Adjunctive Therapy Form of the CRF, respectively).
- Outcome defined as resolved, resolving, ongoing, worsening, death, or unknown.
- Whether the event meets the definition of a SAE (see Section 8.1).

Wherever possible, all AEs, regardless of the seriousness, must be followed through resolution. The completeness and accuracy of the Adverse Event Form will be checked by the study monitor who visits the site.

#### 8.4.2. Causality Assessment

Part of the adverse event documentation will involve the investigator making a causality assessment. To promote consistency between investigators, the following guidelines should be taken into consideration along with good clinical judgment when determining the relationship of Photorin®, devices and laser light application to adverse event.

The following criteria can be used to evaluate the causal relationship between PDT-Photofrin® and the AE.

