## 1.2. Newly Developed Bronchoscopic Technologies

Newly developed bronchoscopic technologies such as navigational bronchoscopy, including the electromagnetic navigation bronchoscopy (ENB) system, and radial endobronchial ultrasonography (REBUS) have shown that reaching peripheral lung lesions and obtaining diagnosis in humans is both feasible and safe (Eberhardt et al., 2007; Wang Memoli et al., 2012; Brownback et al., 2102; Jensen et al., 2012; Loo et al., 2014; Al-Jaghbeer et al., 2016). In a retrospective chart review of 98 ENB procedures in 92 patients, the diagnostic yield was 60% with a 6% pneumothorax rate (Al-Jaghbeer *et al.*, 2016).

The results of a meta-analysis that included 19 studies totalizing 1,106 patients with peripheral lung nodules reported a total of 40 (6%) pneumothoraces that occurred in 681 procedures, in which two cases were induced using transbronchial biopsy, otherwise, no pneumothorax was ENB procedure-related (Zhang *et al.* 2015). In addition, minor or moderate bleeding was reported in seven cases, and two post-procedure respiratory failure cases were recorded, none of them requiring specific treatment. Other adverse events included two of chest drainage, five of chest pain, three of fever, seven of sore throat, four of hemoptysis, and four of emesis, attributed to sedation or biopsy procedure.

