#### *5.2.1.2. PDT Bronchoscopy (Study Day 3, 40-50 Hours post Photofrin® injection)*

Subjects will return to the institution on Study Day 3 (40-50 hours post Photofrin® injection) for the PDT bronchoscopy procedure. The following assessments will be performed.

1. Vital signs (pulse, blood pressure, temperature, and respiration rate).
2. ECOG Performance Status.
3. Under general anesthesia or deep sedation
  - a. Subjects will undergo a flexible bronchoscopy with navigation guidance to confirm the location and the size of the lesion with the use of radial probe endobronchial ultrasonography (REBUS). This will be captured by video.
  - b. The investigator will select the optical fiber diffuser length to match the tumor length.
  - c. Once the desired placement of the probe is confirmed by REBUS, the investigator will remove the REBUS probe and will insert the selected optical fiber in the lesion under fluoroscopy guidance. This will be captured by video. Exceptionally, the placement of the diffuser adjacent to the tumor for intraluminal activation will be acceptable only if the placement of the optical diffuser in the lesion has been unsuccessful. For larger lesions than 1.5 cm the placement of multiple fibers from different directions will be allowed if feasible.
  - d. After the placement of the optical fiber in the lesion, the 630 nm PDT laser will be turned on and will deliver a light dose of 200 J/cm of diffuser length for an exposure time of 8 minutes and 20 seconds using a pre-set total power output. Subjects presenting multiple metastases, only one lesion would be treated.
4. Re-educate the subject on how to manage light exposure.
5. Record concomitant medications and adverse events.
6. Admit subject for a 48-hour hospitalization period.

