#### NO REASONABLE POSSIBILITY

- The AE is definitely not associated with PDT-Photofrin®;
- The AE does not follow a reasonable temporal sequence from PDT-Photofrin® administration;
- The AE does not disappear or decrease on discontinuation of PDT-Photofrin® (dechallenge) and/or does not reappear or increase on repeated exposure (rechallenge);
- The AE is reasonably explained by known characteristics of the subject's clinical state, history, environment, other therapy administered to the subject (drug or non-drug); and/or
- The AE may be caused by reasons other than administration of PDT-Photofrin®.

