## 10. DATA MANAGEMENT AND STATISTICS

### 10.1. Sample Size/Power Considerations

This study is designed to assess the safety of PDT in subjects with solid lung tumors prior to surgical resection and to assess the lung tumor and healthy tissue response to PDT. The intent of this study is to enroll 10 subjects. This sample size has the following precision for estimation of rates of AE's of special interest (AESI). The following table shows historical AE rates for RFA ranging from <1 to ~50%.

AESI	Rate observed with RFA
Pneumothorax	11-52%
Pleural effusion	6-19%
Hemorrhage	6-18%
Pulmonary artery pseudoaneurysm	0.2%
Needle tract seeding	0.3-0.7%
Cavitation	14%
Bronchopleural fistula	0.6%
Pneumonitis	0.4%

The sample size of N=10 has precision for estimation of AE rates for estimates ranging from <0.01 to ~0.5 as shown in the following list. Precision is measured by 1-sided 95% upper confidence limit (CL) on the estimated AE rate *via* exact binomial distribution. PDT is expected to have lower AE rates than RFA, so, for example, for a RFA historical rate of 0.27 (27%), if no such AE's are observed on PDT, then the TRUE underlying PDT rate is lower than 0.27 with 95% confidence since the upper 95% CL is 0.26 - indicated by "\*" in the list below.

No. of AESIs	Rate	Upper 1-sided 95% confidence limit
0	0.00	0.26*
1	0.10	0.39
2	0.20	0.51
3	0.30	0.61
4	0.40	0.70
5	0.50	0.78

The study will be suspended and re-evaluated from a safety standpoint if 20% of the subjects experience a serious adverse event that is related to PDT.

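### Adverse events get one relationship rating against PDT-Photofrin that does not say whether the study bronchoscopy and sedation are included, and the SAP narrows it to the drug alone

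*Protocol*

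**What the plan says.** Protocol 8.4.2 gives guidance on the relationship of Photofrin, "devices and laser light application to adverse event". It then supplies one set of criteria, not one per component: "The following criteria can be used to evaluate the causal relationship between PDT-Photofrin" and the event. The answer is either Reasonable Possibility or No Reasonable Possibility.

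Two of the criteria for No Reasonable Possibility matter here. One is a reasonable explanation by the subject's condition or by "other therapy administered to the subject (drug or non-drug); and/or". The other is: "The AE may be caused by reasons other than administration of PDT-Photofrin".

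Protocol 5.2.1.2 requires a flexible navigational bronchoscopy with radial ultrasound and fiber insertion on Day 3: "Under general anesthesia or deep sedation". The primary diagnosis is complete before consent (4.1, 5.1), so this bronchoscopy is a study procedure.

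Relatedness is used in three places:
- Protocol 10.5.3 tabulates adverse events by this two-level relationship.
- SAP 5.4.11.1 defines an event as treatment-related when its relationship to the study drug, which it identifies as PHO, is recorded as a reasonable possibility. It then summarizes related and serious related TEAEs.
- Protocol 10.1, repeated in SAP 3.1, suspends the study for re-evaluation if 20% of subjects "experience a serious adverse event that is related to PDT".

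**The concern.** Suppose a subject has a pneumothorax or a respiratory event on Day 3 and the investigator attributes it to the scope or the sedation. One site can treat that as another therapy, or as a cause other than PDT-Photofrin, and rate the event unrelated. Another can regard the bronchoscopy as part of PDT and rate it related. Both follow the text, although 8.4.2 says its purpose is consistency between investigators. Under the SAP wording, even harm from the light or the fiber could be left out of the related tables, because the definition refers only to the drug.

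The treatment being studied is PDT delivered through navigational bronchoscopy (Protocol 1.4). With 10 subjects, one classification changes the related-event summary visibly, and two could decide whether the suspension count is reached.

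**Working it through.** **Where the documents place the bronchoscopy**

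| Place | What it implies |
|---|---|
| Protocol synopsis, duration of treatment | Treatment is Photofrin plus a single bronchoscopy-PDT: bronchoscopy inside |
| Protocol 5.2.1.2, title | The Day 3 procedure is called PDT Bronchoscopy: bronchoscopy inside |
| Protocol 3.1 | A course consists of the injection and one light application; bronchoscopy is the route: status open |
| Protocol 8.4.2, objects of rating | Photofrin, devices, laser light: bronchoscopy and sedation not named |
| Protocol 8.4.2, criteria | Other drug or non-drug therapy, or other reasons, support an unrelated rating: bronchoscopy may fall outside |
| Protocol 6.2.3 | The device inventory concerns optical fibers: the bronchoscope is not named as a device |
| SAP 5.4.11.1 | Relationship to the study drug (PHO): devices and light also dropped |
| SAP section 6 | No changes from the protocol-specified analyses |

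The first two rows and the criteria row point in different directions, and no passage settles the matter. The SAP definition does not match 8.4.2.

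**The plan's own limits.** Protocol 10.1 uses the exact one-sided 95% upper limit with n = 10, that is, the 0.95 quantile of Beta(x+1, 10−x).
- x = 0: 1 − 0.05^(1/10) = 0.2589, stated as 0.26.
- x = 1: 0.3942, stated as 0.39.
- x = 2 to 5: 0.5069, 0.6066, 0.6965, 0.7776, stated as 0.51, 0.61, 0.70, 0.78.

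All six reproduce.

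**Illustration 1: could an access event occur at this sample size?** Protocol 1.2 cites a chart review of diagnostic electromagnetic navigation bronchoscopy in which "the diagnostic yield was 60% with a 6% pneumothorax rate". Assume that 6% carries over.
- Expected events: 10 × 0.06 = 0.6.
- P(at least one) = 1 − 0.94^10 = 0.461.
- P(at least two) = 0.461 − 10 × 0.06 × 0.94^9 = 0.461 − 0.344 = 0.118 (from unrounded terms).
- If the rate is 3% instead, P(at least one) is 0.263. If it is 15%, it is 0.803.

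One such event rated related rather than unrelated moves the related proportion from 0/10 to 1/10. The upper limit then moves from 0.26 to 0.39, if limits are computed for related events.

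**Illustration 2: the suspension count.** Read the 20% rule as at least 2 of 10 subjects. The documents give no SAE rates, so both rates here are assumed: 5% per subject from drug or light and, independently, 6% from access.
- Access SAEs counted: p = 1 − 0.95 × 0.94 = 0.107, and P(at least 2 of 10) = 0.291.
- Access SAEs rated unrelated: p = 0.05, and P(at least 2 of 10) = 0.086.
- With assumed access SAE rates of 3% to 15%, the first figure runs from 0.182 to 0.601. The second stays at 0.086.

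**The case against.** Four objections have force.

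- **The primary result does not depend on relatedness.** Every adverse event is recorded whatever its cause (Protocol 8.4.1). The primary endpoint is incidence of adverse events, and SAP 5.4.11.1 attaches the exact limit to the TEAE table by system organ class and preferred term. A pneumothorax rated unrelated still counts there as 1/10 with limit 0.39. A reader might infer that access harm could vanish from the safety result. The documents do not support that.
- **Bronchoscopy can be read as part of PDT.** The synopsis and the title of 5.2.1.2 favor this, devices plausibly covers fiber insertion, and a Day 3 event meets the temporal criterion for a reasonable possibility. It would be too strong to say the protocol excludes the bronchoscopy. It leaves the question open.
- **The 6% is a weak input.** It counts any pneumothorax in diagnostic procedures. The meta-analysis also cited in Protocol 1.2 reports 40 pneumothoraces in 681 procedures, and it attributes two to transbronchial biopsy and otherwise none to the navigation procedure. The 11-52% in 10.1 is for radiofrequency ablation, which Protocol 1.1.1 describes as percutaneous. The documents do not show that pneumothorax here would be mainly an access complication, and not every pneumothorax is serious.
- **Some harms can already be separated.** Photosensitivity is summarized on its own. Listings give term and start date, and details of the light application are listed. An independent DSMB reviews safety data, and 8.4.3.1 has a 24-hour reporting clause for SAEs associated with study procedures. So it would be wrong to say that drug, light and access harm cannot be told apart. But none of these provides an attribution by component, and effects of all three can overlap after Day 3.

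The adverse event form is not among the documents, so the single rating is inferred from Protocol 8.4.2 and 10.5.3 and SAP 5.4.11.1. The inconsistency between 8.4.2 and the SAP remains whatever the form looks like.

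**Conclusion.** The point holds as an undefined scope plus a mismatch between protocol and SAP. The plan does not say whether PDT-Photofrin includes the study bronchoscopy and sedation, and its criteria allow sites to rate the same access event differently. The SAP narrows treatment-related to the drug without declaring a change. The outputs exposed are the relationship tables, the related and serious-related TEAE summaries, and the suspension count. All-cause incidence and its limits stand.

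At N = 10, one reclassified event moves the related proportion by 10 percentage points. The 46% chance of at least one event is an illustration that rests on carrying over a diagnostic-bronchoscopy rate. The contrast of 0.291 with 0.086 rests on assumed SAE rates. Neither is a forecast for this trial. A change to the form and the wording is warranted; a change to the primary analysis is not.

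**What to change.** - On the adverse event form and in Protocol 8.4.2, record relationship separately to (a) Photofrin, (b) laser light or optical fiber and (c) study bronchoscopy including anesthesia or sedation.
- In SAP 5.4.11.1, define treatment-related as Reasonable Possibility for any of the three, and list or tabulate each component. Record the alignment in SAP section 6 if it departs from the protocol text.
- Reconcile Protocol 8.4.2, Protocol 10.1 (with SAP 3.1) and SAP 5.4.11.1 so that related to PDT has one stated meaning. Which components count towards suspension is for the sponsor and the DSMB to state; the statistical requirement is that it be stated once and applied at every site.

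The cost is two extra fields per adverse event (if the form now has one), short edits to both documents, and possibly a slightly higher treatment-related incidence.

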#### NO REASONABLE POSSIBILITY

- The AE is definitely not associated with PDT-Photofrin®;
- The AE does not follow a reasonable temporal sequence from PDT-Photofrin® administration;
- The AE does not disappear or decrease on discontinuation of PDT-Photofrin® (dechallenge) and/or does not reappear or increase on repeated exposure (rechallenge);
- The AE is reasonably explained by known characteristics of the subject's clinical state, history, environment, other therapy administered to the subject (drug or non-drug); and/or
- The AE may be caused by reasons other than administration of PDT-Photofrin®.

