STUDY PROCEDURES: Eligible subjects will undergo screening evaluation conducted during the 30 days prior to enrollment. This phase will involve medical evaluation and eligibility assessment. Upon successful baseline evaluations, subject will be enrolled to receive PHO 2 mg/kg as a slow intravenous injection over 3 to 5 minutes. Forty to 50 hours after the injection, a laser light at a dose of 200 J/cm (630 nm wavelength) of diffuser length will be delivered to the tumor through navigational and or peripheral ultrasound guided bronchoscopy. Subjects will be hospitalized for 48-72 hours after PDT for safety monitoring. Ten to 15 days after PDT, all subjects will undergo surgery as per standard of care. Macroscopic and microscopic examinations of the tumor and surrounding healthy lung tissue will be evaluated to determine the effect of PDT on the tumor and the healthy/non-tumor lung tissue. Macroscopic examinations will be performed at the local institution. Microscopic examinations will be performed by a central reader. Follow-up assessments will include some or all the following procedures: physical exam; vital signs evaluation; body weight measurement; chest CT; chest X-ray; performance status; and clinical laboratory testing. All subjects will be asked general questions about the occurrence of adverse events, concurrent medical conditions, use of adjunctive therapy/procedure, and intake of concomitant medication.	
PLANNED STUDY ENROLLMENT DATES: Q2 2017 to Q1 2018.	
TEST PRODUCT, DOSE AND MODE OF ADMINISTRATION: Porfimer sodium (Photofrin®) 2.0 mg/kg delivered intravenously.	
DURATION OF TREATMENT: This study is a one-time administration of Photofrin® and one-time use of navigational with or without radial ultrasound bronchoscopy-PDT. Duration of Follow-Up: Subjects will be followed for 3 months post-surgery.	
MAIN CRITERIA FOR INCLUSION: 
 
1. Male or female subject is eighteen years of age and older (but less than 80 years of age).
 
2. Subject is diagnosed with primary or metastatic tumor < 5 cm located in peripheral lung that can be completely resectable (R0).
 
	

3. Subject is a candidate for surgical resection.
4. Subject is a candidate for bronchoscopy.
5. The tumor is accessible for unrestricted illumination of PDT.
6. Subject is deemed likely to survive for at least 3 months.

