#### REASONABLE POSSIBILITY

- The AE follows or may follow a reasonable temporal sequence from PDT-Photofrin® administration;
- The AE disappears or abates upon discontinuation of PDT-Photofrin® (dechallenge) and/or reappears or worsens on repeated exposure (rechallenge);
- The AE cannot be reasonably explained by known characteristics of the subject's clinical state, history, environment, other therapy administered to the subject (drug or non-drug); and/or
- The AE is a known effect of PDT-Photofrin®.

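### One bullet in protocol 8.4.2 lets an adverse event be rated No Reasonable Possibility merely because another cause is possible

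*Protocol*

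**What the plan says.** Protocol 8.4.2 states that its aim is consistent rating between investigators. It says that the "guidelines should be taken into consideration along with good clinical judgment when determining the relationship of" the drug, the devices and the laser light to an event. Two lists follow, each joined by and/or. Nothing says how many bullets are needed or which list prevails.

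- **No Reasonable Possibility.** Five bullets: definite absence of association; implausible timing; "The AE does not disappear or decrease on discontinuation of PDT-Photofrin" (with the matching rechallenge clause); "The AE is reasonably explained by known characteristics of the subject's clinical state, history, environment, other therapy administered to the subject"; and "The AE may be caused by reasons other than administration of PDT-Photofrin".
- **Reasonable Possibility.** Four bullets: "The AE follows or may follow a reasonable temporal sequence from PDT-Photofrin" administration; "The AE disappears or abates upon discontinuation of PDT-Photofrin" (with rechallenge); other factors do not reasonably explain the event; and "The AE is a known effect of PDT-Photofrin".

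Protocol 10.5.3 tabulates events by these two categories only. SAP 5.4.11.1 calls an event treatment-related if the CRF records Reasonable Possibility. It uses that for the treatment-related and serious treatment-related TEAE summaries. Protocol 10.1 and SAP 3.1 suspend the study if 20% of subjects have a serious event related to PDT. Neither says which rating is counted.

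**The concern.** The last bullet of the No Reasonable Possibility list sets a lower bar than its heading. It is met as soon as another cause is conceivable, yet such a cause can exist while a reasonable possibility of relatedness remains. The list already has a proper other-cause criterion, which asks that other factors reasonably explain the event. The final bullet makes that criterion redundant, because any event that other factors reasonably explain may also be caused by them.

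The trial's setting makes the weak bullet easy to meet. Every subject has a lung tumor, and protocol 5.2.2 schedules resection for all subjects 10 to 15 days after PDT. At about five sites and about 10 subjects, guidance that admits opposite ratings of one event can change the related-event tables. The bullet's pull is toward not related.

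**Working it through.** **1. The plan's own figures.** Protocol 10.1 and SAP 3.1 give one-sided 95% exact upper limits for 0 to 5 events in 10 subjects. With x events, the limit is the 95th percentile of a Beta(x+1, 10−x) distribution. For x = 0 it is 1 − 0.05^(1/10) = 0.2589. For x = 1 to 5 it is 0.3942, 0.5069, 0.6066, 0.6965 and 0.7776. These round to the stated 0.26, 0.39, 0.51, 0.61, 0.70 and 0.78. No stated figure is in dispute; the point concerns wording.

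**2. Pairing the bullets.** Three bullets in each list are opposites: timing, dechallenge/rechallenge, and whether other factors reasonably explain the event. Definite non-association and known effect stand alone, but each fits its heading. The bullet on merely possible other causes also stands alone, and it does not fit its heading.

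**3. Where the bullet decides the rating.** Take an event with plausible timing that is not definitely unrelated. Set dechallenge/rechallenge aside, since "This study is a one-time administration of Photofrin" and there is no continuing treatment to withdraw. Three situations remain.

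| Other cause | No Reasonable Possibility bullets met | Reasonable Possibility bullets met | As written | Bullet deleted |
|---|---|---|---|---|
| None possible | none | timing; not explained | Reasonable Possibility | unchanged |
| Possible, but not a reasonable explanation | the last bullet only | timing; not explained | either | Reasonable Possibility |
| Reasonably explains the event | the explanation bullet and the last bullet | timing | judgment | judgment |

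The bullet matters in the middle row. A hypothetical example is a pleural effusion on the Day 5 chest X-ray. The tumor could have caused it, but nothing in the record points there. One investigator relies on the last bullet, another on timing and the lack of an explanation. Both have followed 8.4.2. Without the bullet the lists agree. In the bottom row, which covers many post-resection events, the weighing stays with the investigator. If timing is implausible, the timing bullet already supports No Reasonable Possibility and the last bullet is not needed.

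**4. What one rating moves.** With 10 subjects, one subject is 1/10 = 10 percentage points of any related-event incidence. If the suspension rule used this rating and a denominator of 10, the threshold would be 0.20 × 10 = 2 subjects. Re-rating one of two subjects, each with a single qualifying event, would take 20% to 10%. Both conditions are assumptions. If the denominator were subjects treated so far, 1 of 5 would already be 20%.

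**The case against.** The strongest reply is that the lists are guidance, not an algorithm. An investigator reads each bullet under its heading and applies clinical judgment. That stands, and it limits the point to a risk. It does not justify a bullet that says less than its heading in a section meant to align raters.

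The reach is also limited. All-cause AE incidence and the exact limits do not depend on relatedness. SAEs are reported regardless of relationship (protocol 8.4.3.1), and the DSMB reviews safety data (8.6). SAP 5.4.11.1 lists every event with its relatedness, monitors check the AE form (8.4.1), and an eCRF completion guideline is planned (10.2). All this stands.

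Several stronger readings are tempting, but the documents do not support them:

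- **Related-event rates are biased downward.** No misrating rate can be taken from the documents.
- **Almost every event is ambiguous.** Five yes/no features (timing, dechallenge, reasonably explained, other cause possible, known effect) give 32 profiles, or 24 once the 8 that are reasonably explained with no possible other cause are removed. If any one bullet suffices, 21 of 24 meet both lists. These are unweighted combinations, not event frequencies. Without the bullet the count is still 19: No Reasonable Possibility alone fails in 4 profiles, Reasonable Possibility alone in 1. Most of that overlap comes from mixed answers that judgment must weigh.
- **Days after resection measure the problem.** They are 90/108 = 83% to 90/103 = 87% of study days, but days are not events. Likewise, the chance that exactly 2 of 10 subjects qualify belongs to any 2-of-10 rule, however causality is worded.
- **An event meeting both lists should default to related.** That would class events well explained by the resection as related whenever timing is plausible.
- **The SAP's highest-relationship rule settles it.** That rule chooses among events already rated; it does not rate one event.
- **The dechallenge/rechallenge bullets should go too.** They rarely help after one administration, but the repeated Light Challenge (5.2.3.2 and 7.1) resembles re-exposure for photosensitivity, so deleting them is debatable.

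**Conclusion.** The point holds as a defect in one stated criterion. The bullet allows No Reasonable Possibility on the strength of a merely possible alternative, contradicts the sense of its heading, and makes the stricter explanation bullet redundant. The result is a risk of inconsistent rating or under-attribution in the treatment-related and serious treatment-related TEAE summaries. The suspension rule is exposed only if it uses the same rating, which the documents leave open.

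The frequency of misrating cannot be estimated. The only firm statement of size is that each affected subject moves a related-event incidence by 10 percentage points at 10 subjects. The primary all-cause assessment is untouched, so this is a change worth making rather than a threat to the trial's main result.

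**What to change.** In protocol 8.4.2, delete the last bullet of the No Reasonable Possibility list and move the and/or connector up accordingly. The other-cause criterion is then the mirrored pair: other factors reasonably explain the event, or they do not. Leave the remaining bullets and the role of clinical judgment as they are.

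In protocol 10.1 and SAP 3.1, state that the relationship recorded under 8.4.2 is the one counted as related to PDT, with the 20% threshold unchanged.

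The cost is a wording amendment, with no new data. The downside is that some more events may be rated related, and the suspension rule could be met more often if it uses that rating.
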